10.4.7 PLANNED SAFETY AND INTERIM ANALYSES

The study will be monitored by the DSMB as detailed in Section 8.6. Baseline; participant disposition; study drug exposure; and primary and secondary outcome data will be summarized for each study review with a focus on participant safety. While there are study halting rules that will trigger a study review by the DSMB, there are no formal study stopping rules based on the safety review that would trigger permanent study termination without the review and recommendation of the DSMB.

No formal interim analyses for efficacy are planned for this study.

10.4.8 ADDITIONAL SUB-GROUP ANALYSES

No specific sub-group analyses are planned for this study. Any additions of such analyses will be discussed in the statistical analysis plan.

10.4.9 MULTIPLE COMPARISON/MULTIPLICITY

No adjustments for multiple comparisons are planned for the primary efficacy or safety outcomes. For the secondary outcomes, we will group by outcome domain and apply Benjamini-Hochberg (1995) false discovery rate correction to maintain the nominal alpha level of 0.05.

10.4.10 TABULATION OF INDIVIDUAL RESPONSE DATA

Study data will be tabulated and summarized as described in 10.4.1. Additional details will be discussed in the statistical analysis plan.

10.4.11 EXPLORATORY ANALYSES

Certain measures included in the study were added at the suggestion of the Government Steering Committee to harmonize with the Simpson-Saxon study (including the PCL-5). The study plans to analyze all AUD and PTSD measures collected throughout the study and most can be analyzed using similar mixed modeling techniques described above for the secondary outcomes. Additionally, study group comparisons for all AUD and PTSD outcomes will be made across time from baseline to Week 12. All exploratory analyses will be described in the statistical analysis plan.

10.5 SAMPLE SIZE

The sample size for a proof-of-concept study should be large enough to be able to detect a drug effect or surrogate signal, but at the same time expose a minimum number of participants to an experimental drug combination in a reasonable timeframe within a restricted budget. Sample size was determined based on sample sizes used in similar double-mask, placebo-controlled studies of AUD and PTSD, and based on the estimated recruitment rate over the allotted enrollment timeline.

With these factors in mind, we plan to enroll approximately 180 participants to allow for screen failures/dropouts prior to randomization.

With respect to sample size, the goal is to obtain at least 90 participants randomized to either of the two retained arms (XRNTX/2mg BUP arm and PLACEBO arm). Recruitment will occur over a 24-month enrollment period. If this goal is met with time left in the enrollment period, sites will be allowed to randomize additional participants but will not exceed the original planned sample size of 135 randomized participants across all 3 originally planned study arms.

To ensure balance within each treatment group we will use stratified randomization on site, presence/absence of concomitant antidepressants, and gender. We plan to use blocking within each stratum of the randomization scheme to balance treatment assignments. We estimate that attrition will be approximately 30%. However, all randomized participants will remain in analysis (intent-to-treat) regardless of how long they participate in the study.

For the primary outcome, we assume 90 randomized participants (allowing for screen failures/dropouts) allotted equally among the two study arms and with the success rates shown in the below table. We calculated power for two by two contingency tables for comparisons with each treatment arm and the Placebo arm using a Fisher's Exact test with the Walters approximation applying a nominal two-sided alpha level of 0.05.

In examining our primary outcome, we provide a table of power calculations with a range of potential placebo and treatment responses for a sample size of 45 in each group. The value in orange (0.560) is from the original protocol where the assumption was for an 11% (5/45) positive response rate in the placebo arm and a 31% (14/45) positive response rate in the active treatment arm. All cells shaded in yellow have a value of 0.7 or greater and all cells shaded in green have a value of 0.8 or greater. A sample size of 45 in each group will be able to detect a clinically meaningful difference between groups. For example, a treatment response of ≥38% (17/45) in the active treatment arm (consistent with ALKS-4561 for depression) and ≤11% (5/45) in placebo arm (conceivable in a dual-diagnosed PTSD-alcohol population) would have power of 0.8 or greater. In addition, a situation with more positive responses in the active treatment arm or fewer positive responses in the placebo arm would increase apparent power.

		Treatment Positives									
		24%	27%	29%	31%	33%	36%	38%	40%	42%	44%
Placebo Positives	11	11	12	13	14	15	16	17	18	19	20
		0.860	0.908	0.941	0.964	0.979	0.988	0.993	0.996	0.998	0.999

4%	2	0.714	0.791	0.853	0.900	0.934	0.958	0.975	0.985	0.991	0.995
7%	3	0.556	0.651	0.734	0.804	0.861	0.905	0.937	0.960	0.975	0.985
9%	4	0.409	0.506	0.600	0.687	0.762	0.826	0.877	0.916	0.944	0.964
11%	5	0.286	0.375	0.467	0.560	0.647	0.726	0.795	0.851	0.895	0.929
13%	6	0.192	0.265	0.348	0.437	0.527	0.615	0.696	0.767	0.828	0.877
16%	7	0.125	0.180	0.248	0.326	0.412	0.500	0.587	0.669	0.743	0.807
18%	8	0.081	0.119	0.170	0.235	0.309	0.392	0.478	0.565	0.647	0.723
20%	9	0.057	0.079	0.114	0.163	0.224	0.295	0.375	0.460	0.545	0.628

For secondary hypotheses, we estimate that with equal numbers of participants randomized to each of two treatments groups we will have >80% power to detect a medium effect size (Cohen's $f=0.25$, two-sided alpha level of 0.05) at Week 8. Under optimal conditions, where the correlation between consecutive observations on the same participant is high, and the variability observed between pairs of time points is fairly constant, fewer participants would be required (see table below). Under a less than ideal, worst-case situation where correlation between measurements is low and the variability observed between pairs of time points changes, the proposed sample size is still large enough to detect a moderate effect size, even after accounting for screen failures and drop-outs.

Estimated Sample Sizes per Group for Detecting a Moderate Effect Size at 80% Power				
Modeling Conditions		AUD Outcome	PTSD Outcome	Higher of PTSD/AUD with Screen Failures and Drop-outs (+15)
High Correlation, Constant Variance		42	30	57
High Correlation, Non-constant Variance		42	63	78
Low Correlation, Constant Variance		81	57	96
Low-Correlation, Non-constant Variance		81	120	135

For the Psychophysiological and Fear Conditioning analyses, a total sample size of 90 (45 per group) will allow for a conservative dataset with over 80% power to detect significant differences between the treatment group and the placebo group at the $\alpha = 0.05$ level. Estimates were based on means and standard deviations from previous study samples.

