3 STUDY OBJECTIVES AND OUTCOMES

3.1 Study Objectives

The **specific aim** of this study is to evaluate the effects of sublingual buprenorphine (BUP; Subutex) combined with extended-release injectable naltrexone (NTRX; Vivitrol) in the treatment of comorbid PTSD and AUD.

The **objectives** of this aim are to compare safety and efficacy endpoints in the treatment group versus placebo after 8 weeks (with an additional follow up period extending to 12 weeks).

The study team hypothesizes that the efficacy of BUP/NTRX in the treatment of comorbid PTSD and moderate-to-severe AUD will be greatest in the treatment group followed by a very minimal effect for the placebo group.

SAP version 3.0 was updated to remove the evaluation of the Fear Potentiated Startle (FPS) assessment from this primary SAP. The FPS was changed from a secondary objective to an exploratory objective in SAP version 2.0 due to the pause in the FPS assessment as a result of the COVID pandemic. Exploratory analyses of the FPS assessment will be included and described in a secondary supplemental SAP, as needed.

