6 SAMPLE SIZE DETERMINATION

The sample size for a proof-of-concept study should be large enough to be able to detect a drug effect or surrogate signal, but at the same time expose a minimum number of subjects to an experimental drug combination in a reasonable timeframe within a restricted budget. Sample size was determined based on sample sizes used in similar double-blind, placebo-controlled studies of PTSD and AUD, and based on the estimated recruitment rate over the allotted enrollment timeline. With these factors in mind, we plan to enroll approximately 180 participants to allow screen failures/drop-out prior to randomization of approximately 90 participants across three sites (45 in each treatment arm) within a 24-month enrollment period. We estimate that attrition will be approximately 30%. However, all randomized participants will remain in analysis (intent-to-treat) regardless of how long they participate in the study.

For the primary outcome, we assumed the following success rates based on a similar previous study: Placebo arm 5/45 (11%) or less and 2mg BUP/NLTRX arm 17/45 (38%) or greater. We calculated power for two by two contingency tables for comparison of the treatment and Placebo arm using a Fisher's Exact test with the Walters approximation applying a nominal two-sided alpha level of 0.05. We observe power of 80% or greater for the above assumptions. In addition, a situation with more positive responses in the active treatment arm or fewer positive responses in the placebo arm would increase apparent power.

For secondary outcomes, we estimate that we will have >80% power to detect a medium effect size (Cohen's $f=0.25$, two-sided alpha level of 0.05) at 8 weeks. Under optimal conditions, where the correlation between consecutive observations on the same participant is high, and the variability observed between pairs of time points is fairly constant, fewer participants would be required (see table below). Under a less than ideal, worst-case situation where correlation between measurements is low and the variability observed between pairs of time points changes, the proposed sample size is still large enough to detect a moderate effect size, even after accounting for screen failures and drop-outs.

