7 STATISTICAL / ANALYTICAL ISSUES

7.1 General Rules

All statistical computations will be performed and data summaries will be created using SAS 9.4 or higher. If additional statistical packages are required, these will be discussed in the study report. For summaries of study data, categorical measures will be summarized in tables listing the frequency and the percentage of participants; continuous data will be summarized by presenting mean, standard deviation, median and range; and ordinal data will be summarized by only presenting median and range. Model-based analyses described in Section 9 will be used to obtain point estimates and associated confidence intervals for various measures as well as p-values for comparisons of data between treatment groups. Note: initial models will include the high dose treatment arm; however, if the model cannot converge due to the small number of participants randomized to this arm prior to removal from the study, then the model will only compare outcomes between the low dose and placebo treatments. P-values presented will be based on two-sided tests unless otherwise specified and generally only adjusted for randomization factors (study site, gender, and presence of concomitant antidepressants). Note: in the event a model cannot converge due to small sample sizes for a specific randomization factor, it will be removed from the model. For continuous outcomes, checks of normality will be performed and if required, transformations or non-parametric tests will be employed.

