Statistical analysis modeling will be carried out utilizing SAS/STAT PROC GLIMMIX (SAS Institute Inc. 2017) with the general structure of the SAS code for this model is listed below. Generalized linear mixed models (GLMMs) are a flexible generalization of the linear mixed effect model that allows response outcomes to have an error distribution other than the normal distribution (McCullagh, & Nelder, 1989). The GLMM will employ random intercepts for the between participants' part of the covariance model, and the within participants' part of the covariance model will be initially assumed as autoregressive. The study's primary hypothesis will be tested and associated odds ratio obtained using the 'oddsratio' statement which estimates the risk difference in PSTD+AUD resolution between the treatment arms.

```
proc glimmix data=anlydata;
  class patient treat gender visit site antidepress;
  model primoutcome = treat gender visit site antidepress
    treat*visit/ solution link=logit dist=binary oddsratio;
    random int / type=ar(1) subject=patient;
    ods select parameterestimates Oddsratios;
run;
```

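### Power is computed for Fisher's exact test, but the coded primary analysis works through an odds ratio that cannot reach significance if no placebo participant responds at Week 8, and no fallback is written

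*Protocol*

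**What the plan says.** **Power.** Protocol 10.5 takes 45 participants per arm and computes power "using a Fisher's Exact test with the Walters approximation applying a nominal two-sided alpha level of 0.05". The table crosses 1 to 9 placebo responders with 11 to 20 active responders. The text claims power of at least 0.8 when the active rate is 17/45 or more and the placebo rate is 5/45 or less, and continues that "a situation with more positive responses in the active treatment arm or fewer positive responses in the placebo arm would increase apparent power". SAP 6 repeats the two assumptions, each open-ended in the favourable direction, and states: "We observe power of 80% or greater for the above assumptions".

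**Analysis.** Protocol 10.4.2 specifies a mixed logistic regression with a treatment-by-visit interaction, and a two-sided p-value whose type is not named. The SAP 9.3 code is PROC GLIMMIX with a logit link and binary distribution, and it keeps only the parameter estimates and odds ratios. The SAP says: "The study's primary hypothesis will be tested and associated odds ratio obtained using the 'oddsratio' statement". The same section also describes that output as a risk difference, promises risk-difference estimates and a test of proportions, and defines the link in the model equation as identity.

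**Non-convergence.** SAP 7.1 allows the 8 mg arm to be dropped and says that "in the event a model cannot converge due to small sample sizes for a specific randomization factor, it will be removed from the model". SAP 9.5.1 gives the adverse-event models a chi-square fallback. The primary model has none.

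**The concern.** The test that was powered is not the test that is coded, and the two part company when the placebo arm has no responders at Week 8. Fisher's test handles a zero without difficulty. A logit model cannot: the log-odds in that treatment-by-visit cell has no finite estimate, its standard error grows without limit, and the test statistic goes to zero. The most favourable result the trial could produce would then be non-significant, and SAP 7.7 requires a non-significant primary result to be called inconclusive.

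The region is inside the plan's own range. The table prints rows at 1/45 and 2/45, the 80% claim has no lower limit on the placebo rate, and SAP 3.1 expects an effect in the active group "followed by a very minimal effect for the placebo group". If the gap is found only after unmasking, any rescue test would be chosen with the result in view.

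**Working it through.** **Inputs.** n = 45 per arm, 1:1, two-sided 0.05, and the response rates in the table (Protocol 10.5). Model, link and output from the SAP 9.3 code. Unadjusted Week 8 comparison with complete data, as in the printed table.

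**1. Reproduce the printed figures.** Walters approximation: d = 2·√(n/2)·|asin√(p₂ − 1/2n) − asin√(p₁ + 1/2n)|, power = Φ(d − 1.96) + Φ(−d − 1.96).
- 5/45 against 17/45: d = 2.782, power 0.795, as printed (0.8 only after rounding).
- 1/45 against 11/45: d = 3.041, power 0.860, as printed.

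All 90 cells reproduce to within 0.0005. The row label of the first line is broken in the text available, but its values are those for 1/45. The table is correct for the test it names.

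**2. The odds-ratio Wald test.** With a placebo and b active responders, z = ln[b(n−a)/(a(n−b))] / √(1/a + 1/b + 1/(n−a) + 1/(n−b)).
- a = 1, b = 8: z = 2.253/1.084 = 2.08, significant.
- a → 0: the numerator grows as −ln a and the denominator as 1/√a, so z → 0 for every b.

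At 0/45 against 17/45, Fisher's p is 0.0000024. A risk-difference Wald statistic is (17/45)/√(17·28/45³) = 0.378/0.0723 = 5.23. So the two scales named in SAP 9.3 give opposite verdicts on the same data.

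**3. Power.** The chance of no placebo responders is (1 − p₁)⁴⁵, so Wald power cannot exceed 1 − (1 − p₁)⁴⁵. Enumerating all 46 × 46 outcomes, with a zero cell counted as not significant, gives for 17/45 active:

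| Placebo rate | Chance of zero | Cap | Printed | Wald |
|---|---|---|---|---|
| 1/45 | 36.4% | 0.636 | 0.993 | 0.634 |
| 2/45 | 12.9% | 0.871 | 0.975 | 0.859 |
| 3/45 | 4.5% | 0.955 | 0.937 | 0.919 |
| 4/45 | 1.5% | 0.985 | 0.877 | 0.905 |
| 5/45 | 0.5% | 0.995 | 0.795 | 0.849 |

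- The whole 1/45 row runs from 0.530 to 0.636, against 0.860 to 0.999 printed.
- In the 2/45 row, one of the eight cells printed at 0.80 or more falls below it: 13 active responders, 0.769 against 0.853. The next cell, 14, is 0.807 against 0.900.
- From 3/45 upward no cell printed at 0.80 or more falls below 0.80.
- Down the table, Wald power rises from 5/45 to 3/45 and then falls. The sentence on fewer placebo responses therefore reverses below about 3/45.

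**4. Check with a mixed model.** A random-intercept logistic model was simulated with three visits, arm-by-visit cells and three covariates. Assumptions: random-intercept SD 0.5 or 2.0, equal rates at all visits, no dropout; 250 runs per case, so a Monte Carlo standard error near √(0.8·0.2/250) = 0.025. Power was 0.59–0.67 at 1 against 17, 0.75–0.76 at 2 against 13, about 0.80 at 2 against 14, 0.79–0.82 at 3 against 14, and 0.83–0.84 at 5 against 17. No simulated dataset with an empty placebo Week 8 cell was significant.

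**5. Attrition.** Protocol 10.5 expects about 30%. If that leaves 32 per arm at Week 8 (45 × 0.7 = 31.5; an assumption), the chance of zero placebo responders is (44/45)³² = 48.7% at 1/45 and (43/45)³² = 23.3% at 2/45.

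**The case against.** - **Neither document names a Wald test.** This stands. It is an inference from code that reads the test from coefficients and odds ratios and requests no likelihood-ratio or exact test. On the identity scale in the SAP 9.3 text a zero cell does not block significance: with no placebo responders, 4 active responders suffice, and power at 1/45 against 11/45 is 0.943, above the printed 0.860. The conflict does not remove the problem, because the code is what will be run, but it must be settled first.
- **A reader might infer that the Wald test is weak at low counts in general.** It is not. With 1 observed placebo responder, Wald and Fisher both need 8 active responders; with 2, both need 9. The loss comes only from the exact-zero event.
- **A reader might infer that the stated 80% power fails.** At the planning point it does not; the printed figure there is conservative. In all 60 cells from 4/45 to 9/45, Wald power exceeds the printed value.
- **The sentence on fewer placebo responses is true of the Fisher calculation it accompanies.** This stands too. It misleads only when carried over to the coded test.
- **Rates of 1/45 and 2/45 are the bottom two of nine rows.** This is fair. The expectation in SAP 3.1 is qualitative, not a 2% rate, and Protocol 2.2 reports a strong placebo response in trials of the related combination.

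**Conclusion.** The point holds in a limited form. The powered test and the coded test differ, SAP 9.3 contradicts itself on link and scale, and under the coded logit analysis an empty placebo cell at Week 8 makes a significant result impossible, with no rule to repair it. At 45 per arm, 80% power is lost in the whole 1/45 row and at 2/45 against 13/45, and nowhere else that it is printed. At the planning rates the chance of the event is 0.5%. The consequence is loss of power and a wrongly inconclusive result; there is no added false-positive risk.

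These figures rest on reading the coded test as Wald, on an unadjusted Week 8 comparison and on complete data. The mixed-model simulation, within its noise, gives the same picture. The documents do not support saying that the power table is wrong or that the mixed model should be given up.

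**What to change.** **SAP 9.3.** Reconcile the link and the scale across text, equation and code, and name one primary Week 8 test. Keep the mixed model. Prespecify, before unmasking, that if an arm has no responders (or only responders) at Week 8, the primary p-value and interval come from a method that is valid with an empty cell. Examples are Firth penalised logistic regression on the Week 8 composite with the randomization factors and a penalised likelihood-ratio test, or an exact test stratified by those factors. Check the type I error of the combined rule, since the switch depends on the data. Used alone and unadjusted at Week 8, Firth had size 0.041 to 0.049 at common rates of 5% to 30%; the combined rule has not been computed.

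**Protocol 10.5 and SAP 6.** Recompute the power table for the test and fallback actually used. If no fallback is added, limit the sentence on fewer placebo responses to placebo rates of about 3/45 and above, and the 80% claim to 2/45 and above.

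**Cost.** SAP wording, a few lines of code, a short simulation and a new table; no extra patients or data. In the empty-cell case only, the fallback does not use Week 4 and Week 12 data from participants missing Week 8. Replacing the primary p-value outright with a Week 8-only method would impose that loss in every case, which the size of the problem does not justify.

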10.4.3 ANALYSIS OF THE SECONDARY ENDPOINT(S)

SL-BUP/XR-NTX treatment will be compared with the PLACEBO (PLC) group for the following secondary outcomes:

- Examine differences in baseline psychophysiological measures, severity of PTSD and AUD, and treatment outcomes.
- Examine whether BUP/NTRX improve psychophysiology measures at 8 Weeks (primary endpoint).

- Examine whether the degree of change from baseline to 2-week psychophysiological measures are associated with AUD and PTSD outcomes at Week 8.

*Psychophysiological assessments are optional to not be a barrier to enrollment or randomization.

Continuous data will be analyzed using MMRM with treatment group, gender, site, presence/absence of concomitant antidepressants, and other potential confounders as between-participant factors and visit (categorical) as a within-participant repeated measure. The model will also include the two-way interaction between treatment group and visit. When appropriate, significant differences between treatment groups will be further analyzed with post-hoc comparisons. Adjusted marginal means (also called LS means) will be used to report and test for differences in mean change at Week 8 for the placebo and SL-BUP/XR-NTX groups providing 95% confidence intervals and a p-value for the difference between them.

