9.3.1 CAPS

As mentioned above, the CAPS-5 is a continuous measure that is assessed at baseline and weeks 4, 8, and 12. The CAPS-5 Total Symptom Severity Score ranges from 0 to 80, with higher scores indicating greater PTSD symptoms (Weathers et al., 2018). The treatment effect on the clinical criteria of PTSD as measured by the CAPS-5 over time will be

assessed using a generalized-linear mixed model to account for temporal correlation between measurements and the clustering of the data. This model will include fixed effects for treatment group, visit (as a categorical variable), gender, site, presence/absence of anti-depressants, and a treatment-by-visit interaction term, and a random effect for participant (see model statement below).

$$Y_{ij} = \beta_0 + \beta_1 Visit_{ij} + \beta_2 Site_{ij} + \beta_3 Treatment_{ij} + \beta_4 Gender_{ij} + \beta_5 Anti-depressant_{ij} + \beta_6 (Treatment * Visit)_i + s_i + \varepsilon_{ij}$$

Where Y_{ij} is the j th measure of CAPS-5 in subject i , β_0 is the intercept, β_1 through β_6 are coefficients, s_i is a random subject effect and ε_{ij} is the residual error term.

Statistical analysis modeling will be carried out utilizing SAS/STAT PROC MIXED (Littell, Milliken, Stroup, Wolfinger, & Schabenberger, 2006) with the general structure of the SAS code for this model shown below. Adjusted marginal means (also called LS means) will be used to report and test for differences in mean change in CAPS-5 score at 8 weeks for the placebo and BUP/NTRX groups, providing 95% confidence intervals and a p-value for the difference between them.

```
proc mixed data = anlydata;
  class patient treat gender visit site antidepress;
  model CAPS5_Score = treat gender visit site antidepress
    treat*visit /s;
  random int / subject= patient;
  repeated visit / type=cs subject= patient;
  lsmeans treat*visit;
run;
```

9.3.2 %HDD

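### The secondary sample-size table appears to give three-arm total sizes under a per-group label, and the stated power for a medium Week 8 effect is not supported at 45 per arm unless the baseline-to-Week-8 correlation is high

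*Protocol*

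**What the plan says.** Protocol 10.5 makes its claim for secondary hypotheses on the basis of "equal numbers of participants randomized to each of two treatments groups". It states ">80% power to detect a medium effect size" and defines that effect by "Cohen's $f=0.25$, two-sided alpha level of 0.05) at Week 8". The supporting table is headed "Estimated Sample Sizes per Group for Detecting a Moderate Effect Size at 80% Power". Its entries, in row order, are 42, 42, 81, 81 for the AUD outcome and 30, 63, 57, 120 for the PTSD outcome. A final column takes the higher of the two and adds 15: 57, 78, 96, 135. The text adds that the proposed size suffices even with low correlation and changing variance, after screen failures and drop-outs. SAP 6 repeats the table, this assurance and the claim ("we estimate that we will have >80% power to detect a medium effect size").

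The size is fixed elsewhere in protocol 10.5: "we assume 90 randomized participants (allowing for screen failures/dropouts) allotted equally among the two study arms", that is 45 per arm, with about 30% attrition expected. The same section gives 135 as the original planned total across three arms, now a ceiling.

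The planned analysis is a two-arm contrast. In protocol 10.4.3 adjusted means "will be used to report and test for differences in mean change at Week 8 for the placebo and SL-BUP/XR-NTX groups". SAP 9.3.1 uses them to "test for differences in mean change in CAPS-5 score at 8 weeks for the placebo and BUP/NTRX groups", with baseline entered as one of the visits. SAP 7.2 plans no adjustment for baseline characteristics.

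**The concern.** The table label, the worst-case assurance and the planned size cannot all be right. Read as labelled, the worst-case row asks for 135 per group, or 270 in two arms, against 90 planned. Since 135 is also the three-arm total, the table looks carried over from the superseded design.

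There is also a mismatch of test. The table is framed by correlation between successive observations and variability between pairs of time points, which is repeated-measures language. The sentence it supports is about a medium effect at Week 8. Cohen's f means different things in those two settings.

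This is the only power statement for the continuous AUD and PTSD outcomes. In the SAP these include %HDD and CAPS-5, the two measures examined alongside the composite. Readers, and planners of a later trial, would take from it that a medium Week 8 difference was well covered.

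**Working it through.** **Inputs.** From the documents: f = 0.25, two-sided alpha 0.05, power 0.80, 45 per arm, 30% attrition, CAPS-5 at four occasions (SAP 9.3.1). Not in the documents: the correlation ρ, the sphericity factor ε and the number of occasions m behind the table. These were searched over ρ from 0 to 0.95, m from 2 to 9, and ε from 1 down to 1/(m−1).

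**1. Reproducing the table.** Repeated-measures ANOVA, group-by-visit interaction, k groups, total N:

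- λ = f²·N·m·ε/(1−ρ), df1 = (k−1)(m−1)ε, df2 = (N−k)(m−1)ε
- smallest N, in multiples of k, with power of at least 0.80

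With k = 3:

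| Outcome | m | ρ | ε | Computed total N | Printed |
|---|---|---|---|---|---|
| AUD | 2 | 0.5 | any | 42 | 42, 42 |
| AUD | 2 | 0 | any | 81 | 81, 81 |
| PTSD | 4 | 0.5 | 1 | 30 | 30 |
| PTSD | 4 | 0.5 | 1/3 | 63 | 63 |
| PTSD | 4 | 0 | 1 | 57 | 57 |
| PTSD | 4 | 0 | 1/3 | 120 | 120 |

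Example, last row: λ = 0.0625 × 120 × 4 × (1/3) = 10, with df 2 and 117. With two occasions ε has no role, which explains why the AUD column ignores the variance condition. This was the only combination in the search that matched. No per-group reading, no two-arm total and no pure between-group or within-time test did.

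**2. Same method, two arms.** Required totals are 34 and 66 (AUD), and 24, 50, 46 and 98 (PTSD, in row order). Power at N = 90:

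- AUD: 0.997 (ρ 0.5) and 0.913 (ρ 0)
- PTSD: above 0.99, 0.969, 0.986 and, in the worst case, 0.773 (λ = 0.0625 × 90 × 4 × (1/3) = 7.5, df 1 and 88)

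The worst case therefore needs 98 against 90 planned, before attrition.

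**3. What interaction f = 0.25 means for two arms.** f is the SD of the interaction cell effects divided by the outcome SD, and each cell effect is half the centred between-arm difference.

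- m = 2: a difference in change D gives f = D/4, so D = 1.0 SD.
- m = 4, linear divergence 0, x, 2x, 3x: f = 0.5·x·√1.25 = 0.25, so x = 0.447 and the Week 8 difference is 2x = 0.89 SD.
- m = 4, immediate constant difference D: f = 0.5·D·√(3/16) = 0.25, so D = 1.15 SD.

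**4. The two-arm Week 8 contrast.** For two groups at one time, d = 2f = 0.5. Noncentrality is d√(n/2) = 0.5 × √22.5 = 2.37 on 88 df, and power is 65.0% on raw scores. For change from baseline, the standardized difference is 0.5/√(2(1−ρ)):

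| ρ, baseline to Week 8 | 0 | 0.3 | 0.5 | 0.6 | 0.7 | 0.8 |
|---|---|---|---|---|---|---|
| Power, 45 per arm, complete data | 38% | 51% | 65% | 75% | 86% | 96% |

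The difference detectable with 80% power at 45 per arm is 0.60 SD (0.597 unrounded) on raw scores, or on change at ρ = 0.5. A 0.5 SD difference in change reaches 80% when 0.5/√(2(1−ρ)) = 0.597, that is at ρ of about 0.65. With 30% attrition and observed cases only (45 × 0.7 = 31.5 per arm), power on raw scores, or on change at ρ = 0.5, is about 50%. With complete data, 80% power at d = 0.5 on raw scores needs 64 per arm.

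**The case against.** The strongest reply is that the claim belongs to a repeated-measures framework, as its surrounding wording suggests. On that reading, power above 80% holds at N = 90 with complete data in every scenario except the PTSD worst case. This stands as far as it goes. It does not rescue the worst-case assurance, and an effect of about 0.9 to 1.15 SD between arms is not a medium Week 8 difference, which is what the sentence states.

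A second reply is that 65% is not the power of the planned analysis. This also stands in part: SAP 9.3.1 describes a test of mean change, and power for that depends on a correlation the documents do not give. A reader might infer a flat 65%, but the documents do not support an unconditional figure.

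Third, the source of the table is inferred. Two occasions for AUD does not match SAP 9.3.2, which lists %HDD at baseline and six later visits. The exact match on all eight entries makes the source probable, not documented. The conflict between the label and 45 per arm needs no reconstruction.

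Fourth, a reader might infer that a null CAPS-5 or %HDD result would be taken as excluding a medium effect. The SAP does not support that: section 7.7 treats nonsignificant primary and secondary tests as inconclusive, and 95% intervals are planned.

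Finally, this is a proof-of-concept trial sized partly on similar studies and expected recruitment, and the primary-outcome power table is separate and unaffected.

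**Conclusion.** The point holds in three parts.

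- **Label.** The per-group label conflicts with 45 per arm in every final-column row. The entries are very probably three-arm totals for an interaction test.
- **Worst case.** The assurance fails on the table's own method: 77% at N = 90 for two arms with complete data, and lower with attrition.
- **Week 8 claim.** Power above 80% for f = 0.25, read as a 0.5 SD two-arm difference, is not supported at 45 per arm unless the baseline-to-Week-8 correlation is about 0.65 or higher and data are complete. Across correlations of 0 to 0.8, power for change runs from 38% to 96%. It is 65% at 0.5 and on raw scores, falling to about 50% with the expected attrition.

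These figures assume equal arms, no baseline covariate and, for the attrition figure, observed cases only. A mixed model that uses partial records may recover some of that loss. Adjusting for baseline would give 77% at correlation 0.5 and 84% at 0.6 with complete data, but it is not planned; with 30% attrition the first falls to about 62%. Randomizing up to the ceiling of 135 in two arms (about 67 per arm) would give about 82% on raw scores without attrition, but the stated goal is 90.

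The error lies in the stated justification, not in the planned analysis, and should be corrected.

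**What to change.** In protocol 10.5 and SAP 6:

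1. Delete the table. If it is kept, relabel it as total N, recompute it for two arms (AUD 34 and 66; PTSD 24, 50, 46 and 98), name the test as the group-by-visit interaction, print the assumed correlation, number of occasions and sphericity factor, and state the Week 8 difference that its f implies.
2. Remove the sentence saying that the proposed size is sufficient in the worst case.
3. Replace the Week 8 power statement with the power of the planned two-arm contrast and its assumptions. For example: with 45 per arm, two-sided alpha 0.05 and correlation 0.5 between baseline and Week 8, power for a 0.5 SD difference in mean change is 65% with complete data and about 50% with 30% attrition (observed cases only); the difference detectable with 80% power with complete data is 0.60 SD. Add the range over correlations from 0 to 0.8.

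The cost is a wording change in two documents and a less favourable stated power. No participants, procedures or analyses change.
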